2.1 Objectives

2.1.1. Primary Objective

 To compare the efficacy of a 14-day combination regimen of MF and PM with the standard 17-day course of SSG-PM for the treatment of primary VL patients in Eastern Africa

2.1.2. Secondary Objectives

- To assess the safety of two combination regimens of PM (14 days) and MF (14 or 28 days) with the standard 17-day course of SSG-PM
- To describe the efficacy of the PM (14 days) and MF (28 days) investigational arm
- To describe the pharmacokinetic (PK) profiles of PM and MF (14 days and 28 days regimen) in primary VL patients
- To evaluate parasite clearance in each arm as indicated by direct microscopy and quantitative polymerase chain reaction (qPCR)
- To assess the relationship between PK and PD measurements (parasitological and clinical outcome)
- To describe compliance to MF treatment in an outpatient setting

2.2. Study Endpoints

2.2.1. Primary Endpoint

Definitive cure - cure at 6 months follow up defined as absence of clinical signs and symptoms of VL at D210 and no requirement for rescue treatment during the trial (i.e. no relapse or initial treatment failure).

Confidential Page 22 of 68

2.2.2. Secondary Endpoint(s)

Safety:

Frequency of SAEs and AEs requiring treatment discontinuation.

Frequency and severity of adverse events from the start of treatment through the last visit, at D210.

Efficacy:

Initial cure - cure at the end of treatment (Day 28), defined as recovery of clinical signs and symptoms; absence of parasites (microscopy) and no rescue treatment administered up to and including Day 28.

Probable cure - absence of clinical signs and symptoms of VL at D56 and no prior requirement for rescue treatment.

Pharmacokinetics:

Total and partial blood plasma exposure to PM and MF (bioanalysis performed by a validated LC-MS/MS assay), defined as the area under the concentration-time curve, for MF, during treatment and until the last point of follow-up, and for PM based on full curves both on the first day of treatment (day 1) and the last day of treatment (day 14).

Pharmacodynamics:

Blood parasite clearance over time (qualitative and quantitative), as measured by qPCR from blood samples, from baseline until day 210, and at any suspicion of relapse during the trial.

Tissue parasite loads, as semi-quantified by microscopy and qPCR from tissue samples collected at baseline, at the end of treatment (D28) and at any suspicion of relapse during the trial.

 Compliance to MF treatment in an outpatient setting will be described through patients' hospital records history, drug accountability and PK measurements.

3. Study design and study design rationale

3.1. Study design

This is an open label, Phase III, randomized, controlled, parallel arm multicentre non-inferiority clinical trial to compare the efficacy of a combination regimen of MF and PM with SSG-PM for the treatment of primary adult and children VL patients in Eastern Africa.

In addition, safety of two combination regimens of PM (14 days) and MF (14 or 28 days) will be assessed, and the efficacy of the PM (14 days) and MF (28 days) investigational arm 2 will be described.

The study will be conducted at 5 LEAP sites and 2 MSF sites: Kacheliba in Kenya,

Confidential Page 23 of 68

Amudat in Uganda, Doka, Um El Kher and Tabarakallah (MSF) in Sudan and Gondar and Abdurafi (MSF) in Ethiopia.

The 2 treatment regimens to be tested were as below but with patient's recruitment in arm 2 now discontinued:

- Arm 1: Paromomycin 20 mg/kg/d IM for 14 days combined with oral miltefosine allometric dosing for 14 days
- Arm 2: Paromomycin 20 mg/kg/d IM for 14 days combined with oral miltefosine allometric dosing for 28 days (recruitment is now discontinued in this arm but patients' data available will be analyzed and results described)

The reference arm is the current standard treatment for VL:

Arm 3: Sodium Stibogluconate 20 mg/kg/day IM/IV combined with Paromomycin 15 mg/kg/day IM for 17 days

For patients weighing < 30 kg, an easy-to-use table with allometric dosing scheme by weight, height and sex will be provided to the investigators to define the exact daily dose to be administered. For patients weighing \geq 30 kg, the allometric dose will correspond to the conventional dose in mg/kg. Therefore, in order to simplify the dose calculation, patients weighing \geq 30 to < 45 kg will receive 100 mg/day and patients \geq 45 kg will receive 150 mg/day.

The target population will be VL patients from 4 to 50 years old in order to cover both paediatric and adult population. The limit of 50 years for inclusion is due to higher mortality rate and lower efficacy observed in patients > 50y when treated with SSG-PM in a recent pharmacovigilance program (Kimutai et al., 2017). MF and PM will be administered together, both starting at D1. PM dosage will be 20 mg/kg/d for 14 days administered once-a-day intramuscularly, whereas MF allometric dose will be administered orally BID for 14 days in arm 1 and for 28 days in arm 2.

Patients are hospitalized for 14 days of PM and MF treatment for both arm 1 and arm 2. MF treatment starts at the same time as PM treatment and for arm 2 it used to continue on an out-patient basis until completion of the 28 days treatment.

During hospitalization, compliance to treatment is assured. During this period, patients or parent/guardian will be instructed on MF treatment, the daily dose (morning and afternoon), and the administration with food to avoid or minimize any vomiting. Patients in arm 2 were discharged after 14 days in hospital with clear instructions on how to continue MF treatment, and to return for the Day 28 visit. Compliance during the 14 days treatment outside the hospital was assessed by collecting the empty blisters pack at the day 28 visit and checking for any unused drug. A daily diary was provided to these patients in order to guide them in their treatment schedule at home. Any episode of vomiting reported by the patient was captured by the clinician at day 28 visit. In case of multiple episodes of vomiting or any other adverse events, patients were instructed to come to the hospital for an assessment and management in an unscheduled visit.

Compliance will be further assessed through cross-check with PK data.

SSG-PM combination therapy will be administered for 17 days according to routine VL

Confidential Page 24 of 68

treatment guidelines. Patients will remain hospitalized for the entire duration of SSG-PM treatment. Patients in all arms will come back for the end-of-treatment assessments visit at day 28.

All patients will have pharmacokinetics measurement of MF at D28 and D56 in order to measure end of treatment MF concentration and verify adherence to the treatment. In addition, a subset of patients in Kenya and Sudan will be asked to participate to intensive sampling for both PM and MF PK, defined as the intensive cohort: originally, 40 in each MF/PM combination arms, with selection of 20 pediatric (≥7 to ≤12 yrs) patients and 20 adolescent/adult patients (>12 to ≤50 years). Because of premature discontinuation of arm 2, the number of patients enrolled in this arm in the PK/PD intensive cohort will probably not reach 40, however samples collected will be analysed. Patients who agree to be part of the intensive cohort will be asked to provide a separate written informed consent. The intensive cohort will also have additional qPCR blood samples collected (see section 5.1 Schedule of PK/PD events – Intensive cohort, as well as section 8.4 Pharmacokinetics and Pharmacodynamics Assessments).

3.2. Study duration and duration of subject participation

Each patient's participation in the study will be for approximately 7 months. This will consist of baseline assessments, treatment period (14, 17 or 28 days) and 6 months follow-up. Recruitment for the entire trial is expected to take approximately 32 months assuming that 15 to 30% of all VL patients will meet the eligibility criteria. Therefore, study duration (first patient in to last patient, last visit) is expected to take approximately 39 months. Taking into account the analysis and reporting period, the study shall last at most 45 months.

3.3. Rationale of study design

The strategy to combine one parenteral drug for a short period (PM 20 mg/Kg/d IM for 14 days) with an oral drug for the same or longer duration (MF allometric dosing for 14 or 28 days) was to reduce as much as possible the hospitalization period and to allow the treatment to achieve appropriate exposure and satisfactory efficacy levels for the treatment of primary VL patients. In addition, replacing the toxic SSG with oral MF can bring better safety and a more field-adapted, patient-friendly treatment. NCE candidates won't be fully developed for VL treatment before 2027. Therefore, currently available compounds should be assessed to improve on current recommended treatment and avoid adverse drug reactions observed with SSG.

The primary endpoint of this protocol is cure at 6 months follow up defined as absence of signs and symptoms of VL (and no rescue treatment), aiming to assess efficacy of the regimen of MF combined with PM as compared to the routine VL treatment SSG-PM. The long term follow-up of 6 months is necessary in VL trials due to risk of relapse after a negative test of cure at the end of treatment.

This phase III trial should provide the evidence to determine if the investigational study arm is non-inferior to SSG-PM. Patient tolerability will improve with short course combination regimens that are better tolerated and more patient-friendly.

Safety assessments will include clinical, haematological and biochemistry evaluations at regular time points (day 0, 3, 7, 14, 28, 56 and 210) to ensure safety is adequately

Confidential Page 25 of 68

assessed and treatment failures can be caught.

Samples size estimation is based on the power and precision to estimate the efficacy of definitive cure at 6 months (D210) which is the primary endpoint and main parameter of interest. Taking into consideration the data available on PM monotherapy in East Africa, the results of LEAP 0208 on miltefosine efficacy (Wasunna et al., 2016) and latest efficacy results of MF allometric dose in children in Eastern Africa, the expected efficacy for the combination of PM with MF at the end of 6 months follow-up will be defined as 93%. The margin defined as acceptable for concluding the non-inferiority of the tested treatments compared to the reference arm (SSG-PM, 91% expected efficacy) will be 7%, considering the advantages of MF/PM combination in terms of safety, shorter hospitalization and more patient-friendly.

An interim analysis (IA) will not be performed in this trial. Unfortunately, there is no early marker of cure for VL that would allow an interim analysis using data from end of treatment to predict the outcome at the 6 months follow-up.

Pharmacodynamic parameters of repeated qPCR measurements in blood and in tissue (baseline and EOT), and clinical outcome up to D210 will be assessed to allow for a simultaneous population PK-PD analysis to investigate in detail the drug exposure-treatment response relationship.

[figure not shown]

Figure 1- Overall study design

4. Selection of Subjects

170 patients will be enrolled in each study arm 1 and 3. The total number of patients included in the trial will be approximately 420, taking into account the number of patients randomized to treatment arm 2 before discontinuation of this arm (approximately 80 patients). Patients will be primary VL cases with age range between 4 and 50 years of age.

Confidential Page 26 of 68

In order to meet recruitment target, 5 LEAP sites and 2 MSF sites are included in the trial: Kacheliba in Kenya; Amudat in Uganda; Doka, Um El Kher and Tabarakallah (MSF) in Sudan; and Gondar and Abdurafi (MSF) in Ethiopia.

Sites will be initiated as soon as the required EC/regulatory approvals have been obtained in their respective country.

Approximately 150 VL patients are treated routinely per month in the 7 sites. Based on historical data from previous trials, whereby it is estimated that 15% of patients will not be in the age range of 4-50 years, 20% will be excluded based on lab and/or nutrition criteria, 15% will be female patients not willing or not able to comply with contraception and an additional 30% may not be enrolled for other criterion, the enrollment rate for this trial will thus be approximately 20% of the total number of patients diagnosed with VL. Therefore, the recruitment capacity expected is 20 patients per month when all trial sites are active. Considering a mean approval process of 6-12 months in the countries, the delay in the construction of Umelkher site and the fact that MSF sites have joined the trial at a later stage, the target enrollment of 170 patients per arm is planned to take approximately 32 months.

There will not be a minimum requirement of number of patients enrolled per site; sites are expected to recruit competitively until the total sample size is achieved.

Enrollment will be boosted by increasing patient outreach through local strategies such as active case search.

The following eligibility criteria were designed to select subjects for whom the protocol treatment is considered appropriate. All relevant medical and non-medical conditions should be taken into consideration when deciding whether this protocol is suitable for a particular subject. Eligibility criteria may not be waived by the investigator. Any questions regarding a subject's eligibility should be discussed with the DNDi Medical Coordinator prior to subject's enrollment.

4.1. Inclusion criteria

Subjects must meet **all** of the following inclusion criteria to be eligible for enrolment into the study:

- Patients with clinical signs and symptoms of VL and confirmatory parasitological microscopic diagnosis
- Patients aged 4 to ≤ 50 years who are able to comply with the study protocol.
- Patients for whom written informed consent has been obtained (if aged 18 years and over) or signed by parents(s) or legal guardian for patients under 18 years of age. In the case of minors, assent from the children also needs to be obtained as per each country regulatory requirements

4.2. Exclusion criteria

The presence of any of the following will exclude a subject from study enrolment:

Patients who are relapse cases

Confidential Page 27 of 68

- Patients with Para-Kala azar dermal leishmaniasis grade 3
- Patients who have received any anti-leishmanial drugs in the last 6 months
- Patients with severe malnutrition (for children aged <5 years: weight-for-height WHO reference curves by sex, z score <-3; for patients 5-18 years: BMI-for-age WHO reference curves by sex, z score < -3; for adults >18 years: BMI < 16)*
- Patients with positive HIV diagnosis
- Patients with previous history of hypersensitivity reaction or known drug class allergy to any of the study treatments
- Patients with previous history of cardiac arrhythmia or with a clinically significant abnormal ECG
- Patients suffering from a concomitant severe infection such as TB, schistosomiasis or any other serious underlying disease (e.g. cardiac, renal, hepatic) or chronic condition which would preclude evaluation of the patient's response to study medication
- Pregnant or lactating women
- Female patients of child bearing age who do not accept to have a pregnancy test done
 at screening and/or who do not agree to use contraception from treatment period until
 5 months after the end of treatment (see section 15.2)
- Patients with haemoglobin < 5g/dl
- Patient with signs of severe VL according to Investigator's judgement, requiring an indication for AmBisome therapy based on the clinical manifestations (such as jaundice, bleeding, edema) and clinically significant abnormalities in the following laboratory parameters: haemoglobin, WBC, platelets, liver enzymes (ALT and AST), total bilirubin and creatinine
- Patients with pre-existing hearing loss based on audiometry at baseline
- Patients who cannot comply with the planned scheduled visits and procedures of the study protocol

Confidential Page 28 of 68

^{*} Note: for Ethiopia only: Patients with severe malnutrition (for patients 4-18 years: MUAC cut-off based on MUAC-for-height reference table; for patients > 18 years: MUAC < 170 mm)

5. Schedule of events

Protocol Activities and Forms to Be	Screening		Treat		Follow up visits			
Completed	D-7 to D0	D1	D3	D7	D14	D28 (EOT) +1d	D56 +/- 7d	D210 +/- 14d
Consent form & consent for HIV test	X							
Demographic data and medical history	Χ							
Clinical assessment	X	X	X	Х	X	X	X	X
Nutritional status	Χ							
Audiometric test	Χ				X	X		X
HIV test	Χ							X ¹
Pregnancy test ²	Χ					X	X	Х
Spleen/bone marrow/lymph node aspiration, parasitology assessment (microscopy)	X					Х	X ⁵	X ⁵
Hematology (hemoglobin, WBC with differential, platelets)	X		х	Х	Х	Х	X	Х
Biochemistry analysis (AST/ALT, bilirubin, creatinine)	Х		Х	Х	Х	Х		
Biochemistry analysis (Albumin)	X					Х		Х
ECG ³	Х			Х	Х	Х		
Assessment for PKDL	Х					X	X	Х
Blood sample for miltefosine PK ⁴					X	X	X	
Tissue (bone marrow/spleen/lymph node) and blood sample for PD (qPCR)	Х					х	X ⁵	X ⁵
Treatment arm 1		PM QD/MI	= allometric					
Treatment arm 2 – Discontinued						for 28 days		
Treatment arm 3			SSG/PM Q					
Safety assessment	SAEs/non- serious study related AEs		S F	AEs and AE	s monitorin	g during the stu	ıdy	

Confidential Page 29 of 68

- ¹HIV test at D210 will be done only for patients in Gondar and Abdurafi.
- ²Only for woman of child-bearing potential.
- ³ ECG will be performed at baseline and at D14 in all arms, and in addition at D7 and D28 in the reference arm SSG/PM.
- ⁴MF PK assessments at D14 will apply to all patients enrolled in arm 1, while D28 and D56 samples will apply to all patients enrolled in arm 1 and 2. MF PK sample will be collected prior to the morning dose at D14 and D28 (arm 2). D28 (arm 1) and D56 samples will be collected in the morning.
- ⁵ Parasitology and collection of tissue and blood samples for qPCR will be done during the follow-up period after D28 (at D56 and D210) only if clinically indicated (i.e. anytime if suspect of relapse, with reappearance of symptoms and signs of VL).

Total volume of blood to be collected for patient not included in the intensive PK/PD cohort:

Assumptions: Ht= 1mL EDTA, BQ= 2mL dried tube, MF PK= 2mL EDTA, PD= 1mL EDTA. Volume of blood to be collected will be minimized as much as possible, according to the volume of tubes available in the market. The maximum volume to be collected at each study visit will be 6mL.

General note: PK and PD assessments in this schedule of events do not apply to patients included in the intensive cohort (see section 5.1 Schedule of PK/PD events – Intensive cohort).

Confidential Page 30 of 68

5.1 Schedule of PK/PD events - Intensive cohort

40 patients from Kenya and Sudan in each arm 1 and 2 (20 paediatric ≥7 to ≤12 yrs patients and 20 adolescent/adult patients >12 to ≤50 yrs) will be included in the intensive cohort and will have a separate schedule of PK and PD events as described below. Because of discontinuation of arm 2 in protocol v4.0 dated 22 July 2019, the number of patients in arm 2 enrolled in the PK/PD intensive cohort is expected to be probably less than 40.

Protocol Activities and Forms to Be	Screening	Treatment period (day) +/- 1d except for D28							Follow up visits	
Completed	D-7 to D0	D1	D3	D7	D14	D21 ¹	D28 (EOT) +1d		D56 +/- 7d	D210 +/- 14d
Sampling Time-points:										
Blood sample for paromomycin PK ²	X	Х			Х					
Blood sample for miltefosine PK ³	Х	Χ		Х	Х	Χ	Х		X	
Blood sample for PD (qPCR)			Х	Х	X		Х		X ⁴	X ⁴
Sampling Volumes:										
Total EDTA tube blood volume (mL)	4	12	2	4	12	2	4		4	2
Blood volume for hematology (mL)	1		1	1	1		1		1	1
Blood volume for PK plasma (mL)	2	12		2	10	2	2		2	
Blood volume for PD qRT-PCR (mL)	1		1	1	1		1		1	1
Total dried tube blood volume (for biochemistry)	2		2	2	2		2			2
TOTAL BLOOD VOLUME (mL) 5	6	12	4	6	14	2	6		4	4

¹ D21 visit will only be applicable to the subset of patients allocated to intensive PK sampling in arm 2 (collection of this sample is not applicable anymore in this protocol version).

In order to minimize blood volume collected, a subset of patients will be randomly allocated to one sparse PK sampling schedule:

- D1: either 1, 2, 4, 24h or 1, 2, 8, 24h
- D14: either 0, 1, 2, 4, 24h or 0, 1, 2, 8, 24h

The maximum volume to be collected at a study visit will be 14 mL on day 14.

Confidential Page 31 of 68

² PK PM sample at D1 and D14 (arm 1 and 2):

³ PK Miltefosine sample at D1 and D14 will be collected at the same time points as PK PM (according to the sparse sampling scheme the patient is allocated to). 8h sample will be collected always before the 2nd daily dose. PK samples will be collected prior to the morning dose at D7 and D28 (arm 2). D28 (arm 1) and D56 samples will be collected in the morning.

⁴ Blood samples for qPCR will be collected during the follow-up period (at D56 and D210) only if clinically indicated (i.e. anytime if suspect of relapse, with reappearance of symptoms and signs of VL).

⁵Volume of blood to be collected will be minimized as much as possible, according to the volume of tubes available in the market.

6. Enrolment procedures

The study will be conducted in the LEAP and MSF sites. These sites are located in endemic areas of VL and are reference treatment centers in the regions, where routinely VL patients are diagnosed and treated.

Patients may come to the treatment center passively or through referral from health professionals. Referral can be done on the basis of clinical signs and symptoms and/or rapid diagnostic test. In some of the sites, active case detection is performed by mobile teams visiting regularly highly endemic communities. This procedure will be boosted during the inclusion period of the clinical trial.

Subjects between the ages of 4 and 50 years who fulfill the inclusion / exclusion criteria, and from whom informed consent has been obtained (see 15.1 Informed Consent process) will be enrolled in the study. Patients who have entered screening assessments for this trial will be documented in a Patient Screening/Enrolment Log. Each eligible patient will be assigned a patient identification number by the investigator in the site, sequentially, which will be recorded in the Patient Screening/Enrolment Log.

A note describing the ICF signature and enrolment in the trial will also be made in the patient's file.

Patients were originally randomized centrally to treatment in a 1:1:1 allocation ratio using varying block sizes of 6, 9 or 12 subjects in random order. Following discontinuation of arm 2, a 1:1 allocation ratio is now used with varying block sizes of 4, 6 or 8 subjects. Randomization codes will be prepared by the DNDi Data Center in Nairobi and will be accessible through an online system. If the principal investigator has no internet connection available, randomization codes will also be provided by phone.

Treatment should be started within 7 days after the screening assessment. Otherwise compliance with eligibility criteria has to be reassessed (blood tests).

Enrolment status of subjects at each site will be informed weekly by the sites to the study monitor and updated by data centre. Recruitment will stop once 170 subjects have been enrolled in each trial's arm 1 and 3.

7. Study treatments

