8.4.2. Pharmacodynamic Assessments

Parasite load in blood and tissue aspirate (bone marrow or spleen): PD assessment will be based on real time quantitative polymerase chain reaction (qPCR) for *L. donovani* in EDTA blood or tissue aspirate, based on the amplification of kinetoplastid DNA (kDNA) (other *Leishmania* DNA targets may also be considered), to assess the parasite clearance over time during the treatment with two combination regimen of PM and MF or treatment with SSG/PM.

All patients will have qPCR in tissue and blood at screening and at Day 28 assessment; and during follow-up if there is suspicious of relapse.

In addition, the patients (40 in arm 1 and probably fewer patients in arm 2 now this arm is discontinued) in the intensive cohort who consent to have multiple sampling for PK will also have qPCR blood samples collected at D0, 3, 7, 14, 28, 56 and 210.

Approximately 1 ml EDTA whole blood will be immediately separated from blood EDTA samples taken (e.g. for Complete Blood Count or PK analysis) for the qPCR analysis. The blood samples and also the remainder of bone marrow/spleen aspirate sample (optional) will be immediately diluted with DNA stabilizing buffer solution (L6 buffer) and can then be stored up to 2 years at frozen temperature.

Furthermore, additional relevant PD markers will be considered for analysis in order to monitor treatment effect.

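### Sections 5.1 and 8.4.2 disagree on D56 and D210 blood qPCR in the intensive cohort; if sites follow 5.1, the post-D28 part of the clearance endpoint exists only in suspected relapses

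*Combined protocol and SAP*

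**What the plan says.** Four places in the protocol bear on this.

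- **Section 5.1, footnote 4** (intensive cohort): "Blood samples for qPCR will be collected during the follow-up period (at D56 and D210) only if clinically indicated". The footnote explains this as a suspected relapse.
- **Section 8.4.2** starts with a rule for the whole trial: "All patients will have qPCR in tissue and blood at screening and at Day 28 assessment; and during follow-up if there is suspicious of relapse". It then adds, for the intensive cohort ("40 in arm 1 and probably fewer patients in arm 2 now this arm is discontinued"), that these patients "will also have qPCR blood samples collected at D0, 3, 7, 14, 28, 56 and 210". No clinical condition is attached to the last two days.
- **Section 2.2.2** defines the secondary endpoint as blood parasite clearance over time, "as measured by qPCR from blood samples, from baseline until day 210, and at any suspicion of relapse during the trial".
- **Section 5**, footnote 5 of the main schedule, has the relapse-only rule for other patients: "Parasitology and collection of tissue and blood samples for qPCR will be done during the follow-up period after D28 (at D56 and D210) only" when clinically indicated. The general note below that table says that "PK and PD assessments in this schedule of events do not apply to patients included in the intensive cohort" and refers the reader to 5.1.

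Section 3.1 sends the reader to both 5.1 and 8.4 for the cohort's additional qPCR samples.

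**The concern.** Two operative sections give incompatible instructions for the same patients, visits and samples. Both are current text, and the conflict lies in worded statements, so a broken table does not explain it.

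Section 5.1 is the cohort's visit schedule, so a site could reasonably work from it and draw no qPCR blood after D28 unless relapse is suspected. The D56 and D210 results would then come only from patients chosen on a suspected outcome. They could not show whether cured patients stay clear of parasites, which is what an endpoint running to D210 is meant to describe. If some sites followed 5.1 and others 8.4.2, the data would also be missing by site. Samples not taken at these visits cannot be recovered later.

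**Working it through.** **Can the two rules be read together?** Section 8.4.2 states the suspected-relapse rule for all patients and only then lists D56 and D210 as additional sampling days for the cohort. If those two days were also conditional on suspicion, listing them would add nothing to the general rule. Section 2.2.2 has the same structure: a series to D210, plus sampling on suspicion. Footnote 4 matches 8.4.2's rule for patients in general, not its rule for the cohort.

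**Do the stated blood volumes fit routine sampling?** The inputs are the volume rows of 5.1 and the visit list in 15.2.

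- Section 5.1, by visit (screening, D1, D3, D7, D14, D21, D28, D56, D210): 6 + 12 + 4 + 6 + 14 + 2 + 6 + 4 + 4 = 58 mL.
- Section 15.2: 3 × 6 + 12 + 3 × 4 + 14 + 2 = 58 mL. This reproduces the stated maximum of about 58 mL.
- D56: 1 (haematology) + 2 (PK) + 1 (qPCR) = 4 mL. D210: 1 (haematology) + 1 (qPCR) + 2 (biochemistry) = 4 mL. Each visit already includes 1 mL for qPCR.
- With neither follow-up qPCR sample taken: 58 − 2 × 1 = 56 mL.

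Routine sampling therefore needs no blood beyond what is stated.

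**How much data is at stake in arm 1?** Section 8.4.2 schedules 40 × 2 = 80 follow-up blood samples. Under footnote 4 the number depends on how often relapse is suspected, which the documents do not give. As an illustration only, take 7% to 10% of patients. The lower figure is 1 − 0.93, from the expected cure rate for the test combination in 3.3 and 10.1; the upper figure is an assumption.

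- 40 × 0.07 = 2.8 patients
- 40 × 0.10 = 4.0 patients

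On that assumption, about 3 to 4 patients would have any D56 or D210 result, and 90% to 93% of the arm 1 cohort would have none after D28.

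**What is unaffected?** Blood qPCR up to and including D28 does not depend on footnote 4. Section 10.9 derives the clearance rate by log-linear regression on positive counts, and negative follow-up samples from cured patients would not enter that slope.

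**The case against.** The strongest reply is that little of the planned analysis depends on these samples. Section 10.9 uses positive counts and relates the resulting clearance rate to initial and final outcome; it does not use D56 or D210 qPCR status as the predictor. That stands. A reader might infer that footnote 4 makes the clearance endpoint unmeasurable or defeats the planned test of qPCR against outcome. The documents support neither reading: what is lost is the routine description after D28.

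Three further replies also stand in part.

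- The 58 mL is stated as a maximum, so it could include a conditional sample. It shows that routine sampling fits the budget; it does not show which rule was intended.
- No text gives footnote 4 precedence over 8.4.2. The loss is conditional on sites following 5.1.
- The overall failure rate is not a suspected-relapse rate. Under 10.6, failure also covers initial failure, rescue after adverse events, certain deaths and loss to follow-up at or before D56. In the other direction, clinical suspicion can be more frequent than confirmed relapse. The 3 to 4 patients are therefore an illustration and not a derived expectation.

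Finally, correcting footnote 4 does not deliver the endpoint for the whole trial. The cohort covers arms 1 and 2 only, while the objective in 2.1.2 is clearance in each arm. All of arm 3, and 170 − 40 = 130 of the planned arm 1 patients, would still have no routine D56 or D210 qPCR.

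None of this removes the contradiction between 5.1 and 8.4.2.

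**Conclusion.** This is an internal inconsistency that should be corrected. It affects a secondary pharmacodynamic endpoint and leaves the primary comparison untouched. If sites follow 5.1, the D28 to D210 part of the endpoint would exist only in patients selected on suspected relapse, and sustained clearance in cured patients could not be described. Clearance to D28 and the 10.9 slope remain estimable. The size in arm 1 is about 3 to 4 patients with any follow-up result against up to 40. This rests on the assumed 7% to 10% rate of suspected relapse and on sites applying footnote 4 as written. The wording of 8.4.2 and 2.2.2 favours routine sampling as the intended rule, but no document settles the intention.

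**What to change.** Replace footnote 4 of 5.1 with routine blood qPCR at D56 and D210 for every intensive-cohort patient, in line with 8.4.2 and 2.2.2. Keep the clinically indicated rule for tissue samples and for patients outside the cohort. In 2.2.2, state that the post-D28 part of the endpoint applies to the intensive cohort in arms 1 and 2 only. If relapse-only sampling was in fact intended, correct 8.4.2 and 2.2.2 instead, so that the endpoint for routinely sampled patients ends at D28.

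The edit is short, but it changes study sampling. Section 13 requires ethics committee approval before such a change takes effect, and the cohort's separate consent form (15.1) must be checked for these two samples. Beyond that, the cost is up to two extra qPCR assays per cohort patient. The blood stays within the 1 mL per visit and the 58 mL maximum already stated.
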